This study will involve 8 groups of 25 participants each. Groups 1-3 will have diagnoses of SCZ and CUD (SCZ-CUD); Group 4 will have SCZ only, Groups 5-7 will have CUD only and Group 8 will be healthy control participants. Following screening and baseline neuropsychiatric testing, participants will have two tests days (T1 and T2) that will include task-based fMRI, including assessment of RSC, and measuring a number of other parameters including reward responsiveness, mood, craving, symptoms and cognition. The assessments at T1 will be virtually the same for all groups. At T2 Groups 1-3, and Groups 5-7 will be randomly assigned to one of the following conditions prior to the assessments: receiving 15mg of dronabinol and smoking a placebo marijuana cigarette, receiving two placebo capsules and smoking a real marijuana cigarette, or receiving two placebo capsules and smoking a placebo marijuana cigarette. Group 4 and Group 8 will receive no drug or placebo at T2. Those participants receiving drug will have safety assessments before the drug is administered, after the drug is administered but before leaving the research clinic for the day, and again a week later.

2. Objectives & Hypotheses:

List your research objectives and hypotheses.

In this proposal, we seek to confirm and expand upon our pilot, small "N" pharmacology laboratory investigation of the effects of cannabis and the cannabinoid agonist dronabinol in patients with SCZ-CUD.

Aim 1 of this study will assess the status of the BRC in patients with SCZ-CUD and in healthy controls, as well as in those with SCZ (without CUD) and with CUD (without SCZ):

(1a) To confirm that (i) task-related fMRI activity linked to a monetary brain reward probe; (ii) inter-regional resting state functional connectivity; and (iii) a behavioral measure of reward responsiveness will be decreased in patients with SCZ-CUD as compared to healthy controls; and (1b) to explore these measures in those with SCZ (without CUD) and in those with CUD (without SCZ).

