Aim 2 will assess the effects of cannabis and dronabinol on the BRC in patients with SCZ-CUD and in those with CUD (without SCZ): (2a) To confirm whether dysfunctional (i) task-related fMRI activity linked to a monetary brain reward probe, and (ii) inter-regional resting state functional connectivity will be ameliorated when patients with SCZ-CUD smoke a cannabis cigarette, or take a dronabinol pill; (2b) to explore whether a behavioral measure of reward responsiveness will be improved when patients with SCZ-CUD smoke a cannabis cigarette, or take a dronabinol pill; and (2c) to explore the effects of cannabis and dronabinol on these measures in participants with CUD (without SCZ) and to compare the results to those from (2a).

Aim 3 will assess other effects of dronabinol in patients with SCZ-CUD: To determine (3a) whether measures of cannabis craving, mood and negative symptoms will improve; and (3b) whether measures of psychotic symptoms and cognitive deficits will increase (worsen).

By probing BRC dysregulation and testing the effects of smoked cannabis on this dysregulation, this study will help elucidate whether "self-medication" may be an important component of cannabis use in patients with SCZ. Moreover, by further elucidating the physiological effects of dronabinol, this research can lead to development of therapeutic agents, potentially including dronabinol, other cannabinoids or non-cannabinoid agents that may ameliorate a BRC deficiency and thus limit cannabis use in these patients. This is of great importance because, despite the data suggesting that the atypical antipsychotic clozapine (CLOZ) limits cannabis use in patients with SCZ, its side effects discourage many clinicians from using it. Finding new medications, safer than CLOZ, that may be able to limit cannabis use in these patients is thus of great public health importance.

3. Introduction:

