Participants will be studied using the MID task and Paced Motor task linked to fMRI, resting state functional connectivity, and the Probabilistic Reward Task (a measure of reward responsiveness). Additional assessments will include measures of psychiatric symptoms, craving for cannabis, mood, "high", "liking", cognitive measures, extrapyramidal (EPS) side effects of antipsychotic medications, and plasma levels of THC.

Following medical center guidelines, participants will be asked about symptoms of COVID-19, exposure to someone with COVID-19 and travel, and will also be assessed for fever; visits will not occur if they have symptoms or recent exposure. Participants will be required to wear a mask covering their mouth and nose, and research staff will wear protective equipment per medical center guidelines during study visits.

After completing the informed consent process, participants will be screened for study eligibility. The Baseline Neuropsychiatric Testing Visit will occur once participants have achieved 7 days of abstinence from cannabis and other substances. Once participants have achieved 14 days of abstinence, they will be assessed with the fMRI protocol and other measures twice -- at Time 1 (T1) and Time 2 (T2), each separated by a target duration of 7 days (minimum 2 days with no set maximum time interval between scan days) with continued criteria of 14 days of abstinence before T2). At T1, the assessment will occur without any intervention. At T2, the assessment will occur after administration of a double-blinded cannabis cigarette and a placebo pill for participants in Group 1; a double-blinded placebo cigarette and a dronabinol pill for participants in Group 2; and a double-blinded placebo pill and a placebo cigarette to participants in Group 3. Participants in control Groups 4 and 8 will receive no intervention at Time 2. Participants in control Groups 5, 6 and 7 (CUD without SCZ) will be studied in the same fashion as those in Groups 1, 2 and 3, i.e., with an intervention at T2.

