Groups 4 and 8 (control participants with SCZ without CUD, and normal controls): These control participants will follow the same protocol as participants in Groups 1, 2 and 3, except that they will not be given capsules or a cannabis cigarette at T2. Although they will have an intravenous line inserted, but only a single blood specimen drawn to confirm abstinence from THC. If the participant uses nicotine products, blood will also be drawn to assess the person's nicotine level. Control participants with SCZ (Group 4) who are regular cigarette smokers

will smoke a cigarette prior to the fMRI protocol as described for Groups 1, 2 and 3. Normal control participants (Group 8) will not be cigarette smokers.

Groups 5, 6 and 7 (control participants with CUD without SCZ): These control participants will follow the same protocol as participants in Groups 1, 2 and 3, including the intervention at T2. Those who regularly use nicotine products will use these nicotine products prior to the fMRI protocol and have blood drawn to assess the person's nicotine level as described for patients in Groups 1, 2 and 3.

At the end of the T2 testing sessions, participants in Groups 1 - 3 and 5 - 7 will be assessed by an MD to ensure that they are able to safely leave the laboratory. Lorazepam and haloperidol will be available in case of untoward reactions to dronabinol or cannabis. All scans occur at a medical center thus treatment will be available as needed based on the presenting medical issue. If participants are deemed unstable clinically, they will be observed further until stable or they will be admitted overnight. To monitor for reactions from the drug or procedures, all groups will be contacted the day following T2 and again approximately one week after T2 for a brief check-in. At the one-week call, Group 1-3 participants will be assessed for cannabis and other substance use (TLFB), psychiatric symptoms (using items from the PANSS Positive Scale) and adverse events. Group 5-7 participants will be assessed for cannabis and other substance use (TLFB), and adverse events. If participants are having clinical difficulties, we will ensure that appropriate treatment is initiated. Participants will be contacted approximately 30 days after the end of the protocol to assess for any changes in adverse events.

We may repeat assessments in cases of unplanned technical difficulties or need to further evaluate or monitor participants and would compensate accordingly.

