The two sets of intervention effects (specific to SCZ-CUD and CUD alone) will be compared. To determine whether the dual diagnosis patients given cannabis (G1) will show differential changes in fMRI activation in specific ROIs within BRC and in RSC within the BRC between T1 and T2, we will first conduct a Group (G1, G3, G4, G7, G8) by Time (T1, T2) mixed-model repeated measures ANOVA. Predicting a significant omnibus ANOVA, we will next examine planned contrasts to address specific hypotheses: To determine whether cannabis ameliorates BRC dysfunction, we will compare brain activation/connectivity in the patient group given cannabis (G1) to that of the control groups (SCZ-CUD placebo [G3]); (SCZ alone [G4]; CUD alone placebo [G7]; and normal controls [G8]) using a Group (G1, G3, G4, G7, G8) by Time (T1, T2) mixed-model ANOVA followed by pairwise comparisons. The inclusion of Group 4 in this analysis will allow us to examine whether any significant cannabis effect on BRC in Group 1 (G1) is independent of any changes due to repeated testing specific to having a diagnosis of SCZ. Lastly, although not a primary hypothesis of interest, to further explore any potential placebo effect on BRC, we will also conduct a comparison of G3, G4, G7 and G8.

Aim 2b and 2c (Group by Time effects on RR related to cannabis or dronabinol): To explore whether the patients with SCZ-CUD who received cannabis (G1) will show differential changes in RR between T1 and T2 relative to G3, G4, G7 and G8, we will proceed as above for Aim 2a to assess response bias, and analogously for participants who received dronabinol (G2). Similar analyses will be used for Groups 5, 6, 7 and 8, with results compared to those obtained for patients with SCZ-CUD.

Although not aims of the study, we will assess the relationship between THC plasma levels and changes in BRC activation/connectivity following cannabis (G1 or G5) and dronabinol (G2 or G6) using covariance modeling in SPM8; we will conduct analyses to determine whether cannabis (G1 or G5) and dronabinol (G2 or G6) have comparable effects on fMRI BRC activation/connectivity using a Group (G1 or G5, G2 or G6) by Time (T1, T2) mixed-model ANOVA; and we will use cerebral blood flow values obtained from arterial spin labeling MRI as covariates in the ROI analyses of BOLD data to control for any artifactual changes in fMRI signal related to drug-induced influences on CBF.

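### Aim 2a tests the randomised drug effects (G1–G3, G2–G3) as change scores; adjusting the T2 value for the T1 value already collected would be more precise

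*Combined protocol and SAP*

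**What the plan says.** Aim 2a is worded as confirmatory in section 2: "To confirm whether dysfunctional (i) task-related fMRI activity linked to a monetary brain reward probe", together with resting-state connectivity, will be ameliorated by smoked cannabis or dronabinol in SCZ-CUD. The abstract supplies the randomisation: "Groups 1-3, and Groups 5-7 will be randomly assigned to one of the following conditions prior to the assessments". Within SCZ-CUD, G3 (double placebo) is therefore the randomised comparator for G1 (cannabis) and G2 (dronabinol).

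Section 7b (Aim 2a and 2c) runs a five-group (G1, G3, G4, G7, G8) by two-visit mixed-model ANOVA and then planned contrasts: "To determine whether cannabis ameliorates BRC dysfunction, we will compare brain activation/connectivity in the patient group given cannabis (G1") with the four control groups, pairwise. G3 is named first. G4 is included to show "whether any significant cannabis effect on BRC in Group 1 (G1) is independent of any changes due to repeated testing" specific to schizophrenia. The plan also says that "to further explore any potential placebo effect on BRC, we will also conduct a comparison of G3, G4, G7 and G8". Dronabinol is handled in the same way, and similar analyses are planned for CUD alone.

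G4 and G8 are not placebo groups: "Participants in control Groups 4 and 8 will receive no intervention at Time 2", and the Day of T2 text says they follow the same protocol "except that they will not be given capsules or a cannabis cigarette at T2". G7 receives placebo but has CUD without schizophrenia. Covariates are named (cerebral blood flow in section 7b, trauma in section 10, smoking in the note to section 5). The T1 value of the outcome is not among them in any stated analysis.

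**The concern.** When arms are randomised and the outcome is measured before and after, subtracting the baseline is rarely the most efficient use of it. The change score gives T1 a coefficient of one whatever the data say. If T1 and T2 correlate only moderately, this adds T1 noise to the contrast. Regressing T2 on T1 lets the data set the coefficient and targets the same treatment effect.

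What is at stake is precision in the comparison that isolates the drug, with 25 participants per arm. Section 7c says this size can detect d of 0.7 or more for each drug. The T1 scan is acquired anyway, so the added precision needs no extra participants or visits.

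**Working it through.** **Inputs.** 25 per group (section 4, Overview). d = 0.7 as the meaningful effect (section 7c). Assumed, because the documents do not give them: two-sided alpha of 5%, equal SD at T1 and T2 (set to 1), complete data, and rho from 0.3 to 0.8. Section 7c does not say which SD scales d, so both readings are shown.

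**The plan's own figures.** For Aim 1a (75 against 25, d = 0.7), a two-sided 5% t-test gives 85%, which agrees with the stated 80% or more. For Aim 2a no power is stated. A plain 25-against-25 comparison at d = 0.7 gives 68%.

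**Step 1: Group by Time with two visits.** For two groups, the interaction is (G1 at T2 − G1 at T1) − (G3 at T2 − G3 at T1), that is, a t-test on T2 − T1. The per-person variance is 1 + 1 − 2rho = 2(1 − rho).

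**Step 2: ANCOVA of T2 on T1.** The residual variance is 1 − rho².

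**Step 3: ratio.** (1 − rho²) / [2(1 − rho)] = (1 + rho)/2, which is below 1 for any rho below 1. Dividing 25 by this ratio gives the number per arm that a change-score analysis would need for the same precision.

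**Step 4: power.** Noncentral t with noncentrality 0.7 / [SD × √(2/25)], on 48 df (change score) and 47 df (ANCOVA). At rho 0.5: change-score SD 1.000, 0.7 / (1.000 × 0.2828) = 2.47, power 68%; ANCOVA SD √0.75 = 0.866, 0.7 / (0.866 × 0.2828) = 2.86, power 80%.

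| rho | SD, change | SD, ANCOVA | Variance ratio | Equivalent n per arm | Power, change | Power, ANCOVA |
|---|---|---|---|---|---|---|
| 0.3 | 1.183 | 0.954 | 0.65 | 38 | 54% | 72% |
| 0.5 | 1.000 | 0.866 | 0.75 | 33 | 68% | 80% |
| 0.7 | 0.775 | 0.714 | 0.85 | 29 | 88% | 92% |
| 0.8 | 0.632 | 0.600 | 0.90 | 28 | 97% | 98% |

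Pooling the error over the three randomised arms changes these by no more than about one point (for example, 93% instead of 92% at rho 0.7). A simulation of the three arms with 40,000 runs per cell agreed, and both methods rejected a true null in about 5% of runs.

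**Step 5: d read in change-score SDs.** The change score gives 68% at every rho. ANCOVA gives 85%, 80%, 75% and 72% at rho 0.3, 0.5, 0.7 and 0.8.

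**Step 6: why the adjustment belongs only in the randomised arms.** Randomisation makes the T1 means of G1, G2 and G3 equal in expectation, so adjustment removes noise and nothing else. That does not hold against G4, G7 or G8. Under Aim 1a the reward measures "will be decreased in patients with SCZ-CUD as compared to healthy controls", and differences from SCZ alone and CUD alone are left open for exploration. Adjusting for T1 across groups whose true T1 levels differ can itself create an apparent difference at T2.

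**The case against.** The strongest reply is that this concerns efficiency only. The change score is unbiased under randomisation and holds its error rate. The gain depends entirely on a correlation that the documents never report for fMRI activation or connectivity, and it shrinks from about 18 points of power at rho 0.3 to about 1 at 0.8. All of this stands, and it is why the point is minor. The figures also leave out the covariates the plan does name, so they describe a simpler model than the one intended.

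It can also be said that only the interaction is clearly a change-score test, since the wording of the pairwise step would permit a comparison of T2 levels. That is fair, but it does not rescue precision. A comparison of T2 alone has variance 1, against 1 − rho² for ANCOVA, and gives 68% power at d = 0.7 in T1/T2 SDs whatever rho is.

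A reader might infer something stronger: that the plan would let a difference from untreated or healthy controls stand as proof of a drug effect. The documents do not support this. G1–G3 is among the planned contrasts and is listed first, G4 has a stated retest role, a placebo comparison is planned, and no sentence makes a difference from G4, G7 or G8 sufficient. In a simulation with only a placebo shift of 0.3, 0.5 or 0.7 SD of change (assumed sizes), a significant omnibus test with a G1 advantage over G4 or G8, unflagged by the placebo comparison, occurred in 5%, 8% and 6% of trials. G1–G3 itself stayed at 5%.

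Finally, G8 is not dispensable. G1–G3 shows whether the drug does something; whether a deficit moves toward healthy levels needs the healthy group.

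**Conclusion.** The point holds as a cheap improvement of minor severity. In the two randomised SCZ-CUD contrasts, Group by Time is a valid change-score test that gives up precision. Adjusting T2 for T1 cuts the variance to between 0.65 and 0.90 of the change-score variance for rho between 0.3 and 0.8. In power at d = 0.7 in T1/T2 SDs, that is 54% to 72% at the low end and 97% to 98% at the high end.

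This rests on equal SDs at the two visits, complete data, a two-sided 5% test and an assumed rho. It does not show that the planned analysis is biased, nor that Aim 2a is underpowered: on the T1/T2 SD scale, the change score itself reaches 80% once rho is about 0.62.

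**What to change.** In section 7b, estimate G1–G3 and G2–G3 by ANCOVA of the T2 value on the T1 value within the randomised SCZ-CUD arms, using one extracted value per participant and ROI, and say that the drug-effect statement rests on these contrasts. Do the same for G5–G7 and G6–G7 in the exploratory CUD analysis. Keep the Group by Time model with G4, G7 and G8, without baseline adjustment, for retest, placebo and diagnosis context and, through G8, for whether any change moves toward healthy levels. Keep the placebo comparison.

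No new data are needed, but there are costs. There will be a second model beside the existing one. Connectivity must be reduced to prespecified ROI values, whereas section 4 describes seed-to-voxel maps. Section 7b does not list target regions, although the pilot results in section 3 name several that could be used. If rho turns out to be 0.8 or higher, the gain is negligible.

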Scan Days - Day of T1: T1 will occur as soon as possible after at least 14 days of abstinence. Please note that the exact schedule may need to be modified due to unforeseen events, such as participants arriving late or encountering some form of difficulty and participant schedules. Participants who are caffeinated beverage drinkers will be given a caffeinated beverage (coffee, tea, soda, etc) in order to prevent caffeine withdrawal which may affect the brain reward circuit. (The exact schedule of caffeine, nicotine and food intake may need to be varied to account for changes in the schedule.) All patients with SCZ will be asked to take their usual morning antipsychotic medication at approximately the same time as usual. When participants arrive at the hospital for their scan, they will undergo urine/breathalyzer/pregnancy testing and they will be given breakfast (or similar meal as applicable). Assuming confirmation of continued abstinence (and non-pregnant status), an intravenous line will be inserted with a heparin lock to allow for blood draws (to make the conditions similar to T2, in which participants in Groups 1, 2, and 3, and in Groups 5, 6, and 7 are given an intervention (dronabinol or a cannabis cigarette) and have several tubes of blood drawn.) Lidocaine may be applied to or injected into the skin prior to inserting the needle for patient comfort. At T1, a single specimen of blood will be drawn from all groups to assess participant THC level. Also, if the participant uses nicotine products they will be asked to use these nicotine products at specified times and blood will be drawn to assess the person's nicotine level. All participants will be asked to rate their mood. Participants with CUD will be asked to rate their craving, liking and high. Staff will take vital signs. Participants with SCZ will be rated with brief assessments for psychotic and negative symptoms, as well as EPS. At intervals throughout the day, they will again rate their high, liking, mood and craving and their vital signs will be assessed. The fMRI protocol is described below. After leaving the scanner, they will rate their high, liking, mood and craving, their vital signs will be taken and they will be assessed for reward responsiveness, rated for psychotic and negative symptoms, as well as EPS, and brief

cognitive testing (see below) will be performed. A schedule of events explaining which tasks will occur with the various groups is attached.

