Disclosure of financial impact on the participant is critical to informed consent. Insurance cannot be billed for research-related services outside the standard of care or paid for by the funding agency for the study. The department, the study or the participant may be responsible for payment for research-related services. Participants should know which tests, visits, or procedures will be billed to them or their insurance and which ones will be paid by the funding agency for the study or the department.

a) *List tests, visits, and procedures performed for only research purposes. These services are outside the standard of care. They would not be performed if the individual were not a research participant, and may not be billed to a health insurance plan.*

Note: 6a information must also be in "How is this different . . ." section of the consent form.

This is not a treatment study. All tests and procedures for this study are performed only for research purposes outside of standard care and will not be billed to the participant or his/her insurance.

b) List the tests, visits, and procedures that may be standard care, but for which the funding agency for the study is paying.

None

c) Will the funding agency for the study be responsible for the above costs?

Yes No If No, describe who will be responsible (i.e., department or participant).

7. Statistical Methods and Review Statement:

a) Specify the primary endpoint, as well as other endpoint(s).

- Activation of BRC (particularly the nucleus accumbens) in anticipation of monetary reward.
- Resting state connectivity within the BRC
- Scores on the Rewards Responsiveness task

b) State the statistical analysis plan, including all hypothesis tests (e.g., t-test, chi-square), and estimation methods related to the primary endpoint. If a formal protocol for the study exists, page references to the protocol are acceptable.

We will assess participants comprising 8 groups at Time 1 (T1) and Time 2 (T2): Group 1 (G1) –SCZ-CUD given placebo dronabinol and active cannabis; Group 2 (G2) –SCZ-CUD given active dronabinol and placebo cannabis; Group 3 (G3) –SCZ-CUD given placebo dronabinol and placebo cannabis; Group 4 (G4) –SCZ given no intervention; Group 5 (G5) – CUD given placebo dronabinol and active cannabis; Group 6 (G6) –CUD given active dronabinol and placebo cannabis; Group 7 (G7) –CUD given placebo dronabinol and placebo cannabis; and Group 8 (G8) –normal control participants given no intervention.

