Aim 3 a, b (Group X Time effects of dronabinol on "high", liking, craving, mood, negative and positive symptoms, EPS and cognition in SCZ-CUD: These measures (other than cognition) will be taken in patients with SCZ-CUD (G2) prior to the fMRI scan and before dronabinol pill ingestion (Pre) and immediately after the MRI scan is completed (Post). We will conduct additional analyses to test the specific hypotheses that G2 patients will show: (a) improved

mood, reduced negative symptoms and EPS, and no significant change in psychotic symptoms from Pre to Post; and (b) a greater degree of change (from Pre to Post) in these measures than will those in G3, G4, G7, or G8. For cognitive measures, in which we will use assessments at T1 and T2, we will first conduct a Group (G2, G3, G4, G7, G8) X Time (T1, T2) mixed-model repeated measures ANOVA.

c) Justify the sample size, using the concepts of power, type I error, and effect size if applicable. If a formal protocol for the study exists, page references to the protocol are acceptable.

For Aim 1a (i), our pilot fMRI MID data comparing 12 healthy controls and 12 patients with SCZ-CUD yielded a Cohen's d of 1.10 during anticipation of reward for the accumbens ROI. For Aim 1a (ii), our pilot data on group differences in baseline RSC (12 SCZ-CUD; 12 controls), indicated effect sizes ranging from 0.84 to 1.28. For Aim 1a (iii), our pilot data on reward bias revealed a d of 0.77 for the group difference. Based on the above, we expect Aim 1a to be well powered (for 75 patients with SCZ-CUD and 25 normal controls) with effect sizes of $d \geq 0.7$ detectable with adequate power ($\geq 80\%$). For Aim 1b, the fMRI/MID studies of Juckel et al. showed deficient accumbens response during the MID task in patients with

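### Under Aim 3, hypothesis (a) tests dronabinol's benefit by uncontrolled same-day change in G2, and no rule ties a benefit claim to the randomised placebo comparison available within hypothesis (b)

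*Combined protocol and SAP*

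**What the plan says.** Section 7b, Aim 3 a, b, takes the non-cognitive ratings in G2 "prior to the fMRI scan and before dronabinol pill ingestion (Pre) and immediately after the MRI scan is completed (Post"), so both fall on the T2 dosing day. It then names two hypotheses for G2:

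- Hypothesis (a) is improved "mood, reduced negative symptoms and EPS", with psychotic symptoms not changing significantly, all judged from Pre to Post. No comparison group is named.
- Hypothesis (b) is "a greater degree of change (from Pre to Post) in these measures than will those in G3, G4, G7, or G8".

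Section 7b defines G3 as "SCZ-CUD given placebo dronabinol and placebo cannabis". Section 4 (Day of T2) says of Groups 4 and 8 that "they will not be given capsules or a cannabis cigarette at T2". G7 is the double-placebo group with cannabis use disorder but no schizophrenia.

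Section 4 (Day of T1) has the same ratings taken around an undosed scan. Before it, everyone rates mood, participants with cannabis use disorder rate craving, and participants with schizophrenia are rated for symptoms and EPS. "After leaving the scanner, they will rate their high, liking, mood and craving", and symptoms and EPS are rated again. The T2 text carries these procedures over. Within Aim 3, Section 7b uses T1 data only for cognition.

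The labels do not match across sections. Aim 3a in Section 2 asks "whether measures of cannabis craving, mood and negative symptoms will improve". Hypothesis (a) in Section 7b leaves out craving and adds EPS and psychotic symptoms.

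**The concern.** A before-and-after change in one treated group mixes the drug effect with everything else that changes over the session, including the scan, the monetary task and the passage of hours. Placebo capsules and a placebo cigarette are given to G3 so that this can be separated, but hypothesis (a) does not use G3.

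Hypothesis (b) does plan controlled comparisons of the same measures. It leaves three gaps:

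1. The two hypotheses stand side by side. Nothing says that a significant (a) without (b) is not evidence of benefit.
2. Four comparators are joined by *or*, with no statement of which one decides. G4, G7 and G8 differ from G2 in diagnosis and are not randomised against it, and G4 and G8 receive no placebo.
3. Section 4 describes symptom and EPS ratings only for participants with schizophrenia. On that text, G7 and G8 have no such data to compare. The schedule of events is not in the documents available and could differ.

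Section 3 counts gains in mood, craving or negative symptoms as a possible part of the case for a prospective dronabinol trial. That part should not rest on a change that placebo patients may share.

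**Working it through.** **Plan's own figure.** Section 7c gives no sample size, power or alpha for Aim 3, so there is nothing to reproduce. As a check of method, its Aim 1a statement (75 v 25, d = 0.7, power at least 80%) gives 85% by the t distribution at two-sided 5%, which agrees.

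**Inputs.** From the plan: n = 25 per group. Assumed: two-sided 5%, and a session shift δ, in SDs of the change score, that acts in the favourable direction and is unrelated to the drug. The documents give no value for δ, so a range is shown.

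**Hypothesis (a) alone, no drug effect.** The test is a one-sample t on Pre-to-Post change. Noncentrality = δ√25 = 5δ, critical t on 24 df = 2.064, and the false-benefit rate is P(t > 2.064).

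| δ (SD of change) | 5δ | False-benefit rate |
|---|---|---|
| 0 | 0 | 2.5% |
| 0.1 | 0.5 | 7.0% |
| 0.2 | 1.0 | 15.9% |
| 0.3 | 1.5 | 30.2% |
| 0.5 | 2.5 | 67.0% |

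A shift towards worsening makes 5δ negative and puts the rate below 2.5%.

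**G2 v G3, no drug effect.** A shift common to both groups cancels. In 40,000 simulated trials at each of δ = 0, 0.2, 0.3 and 0.5, the false-benefit rate was 2.3% to 2.5%. Requiring both (a) and a significant G2 v G3 difference gave at most 2.4%.

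**Cost in power at a true effect of 0.7 SD of change.**

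- Uncontrolled test: noncentrality 0.7 × 5 = 3.5, power 92%.
- G2 v G3: noncentrality 0.7/√(1/25 + 1/25) = 2.47, critical t on 48 df = 2.011, power 68%. The effect detectable with 80% power is 0.81 SD.
- G2 v G3 with the T1-day change as covariate: residual SD is √(1 − r²), where r is the correlation between the two days' changes. At r = 0.3 the effective d is 0.7/√0.91 = 0.734, power 72%. At r = 0.5 it is 0.7/√0.75 = 0.808, power 80%. Both values of r are assumed, and the degree of freedom spent on the covariate is ignored.

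**The case against.** The strongest reply is that the controlled test is already planned. Hypotheses (a) and (b) are joined by *and* under a heading about group-by-time effects, and (b) includes G3. Read as a joint requirement with G3 deciding, the false-benefit rate stays at or below 2.4%. A reader might infer from (a) that the plan has no controlled test of benefit; (b) shows that this is wrong. What stands is that the text does not state the joint requirement. The pair also cannot work as a simple gate for psychotic symptoms, where (a) predicts no significant change while (b) predicts a greater change in the same list of measures.

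A reader might also blame the caffeinated drink, the meal and the intravenous line for a Pre-to-Post shift. Section 4 narrates all three before the pre-scan ratings, so on that order they belong to Pre. What clearly lies between Pre and Post is the scan with its reward task.

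Nor is T1 an exact undosed copy of T2. It always comes first, has no placebo capsule or cigarette, alone includes the structural scan, and may be run on a shortened schedule. It cannot remove expectancy or order effects, so it is no substitute for G3.

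The false-benefit rates depend on an assumed favourable shift. Section 14 expects assessments to cause some discomfort, boredom, anxiety or fatigue, and a shift that way would make (a) conservative.

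On blinding, Section 4 says that assessment staff are blind to group. The sentence sits in the text on Groups 1–3, so its reach to G4 and G8 is unclear. It does not support a claim that raters will know.

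Finally, none of these measures is among the endpoints listed in Section 7a, and Section 3 puts improved reward-circuit function first when it discusses a later trial. That limits the weight of the point.

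**Conclusion.** The concern holds in limited form. Hypothesis (a) is an uncontrolled within-group test, no rule makes a benefit claim depend on (b), and (b) does not name the deciding comparison. If (a) is reported on its own, 25 patients and a modest favourable session shift of 0.2 to 0.3 SD would give a false benefit in 16% to 30% of trials per measure, rising to 67% at 0.5 SD. The randomised contrast stays near 2.5%. These figures assume two-sided 5% testing and a favourable shift whose size the documents do not give, and they apply only if (b) is set aside. The documents do not support the stronger statement that Aim 3 lacks a controlled comparison. Naming one deciding contrast is still more than tidying, because it replaces an uncontrolled test with a randomised one. The plan should make this change.

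**What to change.** In Section 7b, Aim 3, base any benefit claim on one contrast per measure for mood, craving, negative symptoms and EPS. The contrast is G2 v G3 on the T2 Post value, adjusted for the T2 Pre value and for the same patient's T1-day Pre-to-Post change. State that the T1-day change is a precision covariate and not a control. Report the within-G2 change and the comparisons with G4, G7 and G8 as descriptive, and say for which measures G7 and G8 have data. Bring the measure lists in Section 2 (Aim 3a) and Section 7b into line.

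The change is to wording only, because on the text of Section 4 all the ratings are already collected. The price is the lower power set out in the working, which the T1-day covariate recovers only in part.
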